[figure not shown]

SYNOPSIS (English)	
Title	Pain monitoring after breast biopsy: benefit of e-health
Acronym	BIO-PSY
Pathology	Breast cancer
Protocol codes	Sponsor Code : PRO ICM 2020-06 BIO ID-RCB: 2020-A00836-33 N° NCT : NCT04456920
Study Sponsor	Institut régional du Cancer de Montpellier - ICM Clinical Research and Innovation Department (DRCI) [name] – France Contact Name : Mme [name] Mail : [contact] [contact] [contact]
Clinical trial coordinators	[name] [name] ICM Department of Radiology [contact] E-mail : [contact] Clinical trial co-coordinator : [name] [name], Ph.D ICM Department of Supportive Care [contact] E-mail : [contact]
Methodology and data management Center	Institut régional du Cancer de Montpellier - ICM Biometrics Unit Contact : Mme [name] [contact] E-mail : [contact]
Project manager	Institut régional du Cancer de Montpellier - ICM DRCI - Promotion Unit Contacts : [name] [name] [contact] E-mail : [contact]
Study design	Monocentric, prospective, open-labeled, randomized controlled trial
Trial sites	1 participating center
Number of planned patients	Expected number of patients : 192

Background and Rationale	
Each year, approximately 1500 breast biopsies (1000 microbiopsies and 500 macrobiopsies) are performed in the radiologic department of the Montpellier Cancer Institute (ICM). This exam, which is relatively easy for the radiologist, can however lead to major anxiety for patients. Indeed, previous studies show that about 50% of women undergoing a breast biopsy have significant anxiety affects. Anxiety associated with the risks of biopsy, potential breast cancer diagnosis and/or lack of routine sedation procedures increase patient concerns. Distress prior to biopsy is associated with greater pain and discomfort during the procedure. The psychological distress that persists after the biopsy is related to a worse psychological management of side effects of the biopsy breast (e.g., sensitivity, skin irritation).
 
Limiting apprehension, worry and anxiety induced by the uncertainty linked to the biopsy results and the biopsy-related pain should be an integral part of the medical care through the patient follow-up during, after and until the diagnosis is announced. In light of these challenges, new alternative methods are emerging to enhance patient knowledge, develop procedural skills, improve confidence and mitigate procedural anxiety. However, to our knowledge, few methods have been developed during this period of 'waiting-time'. Currently, only care instructions and a consultation to announce the results (about 10 days after the procedure) are proposed to patients at the end of biopsy. Patients are also encouraged to call if they suspect complications such as infection or bleeding.
 
In this context, we propose to integrate a pain management after biopsy via e-health system through the patient's medical care. Radiologist/patient communication could have an impact on patients' anxiety and health-related issues, given the challenging nature of discussions around need for breast biopsy and potential implications of the results. Indeed, paying attention and focusing on symptoms as patients experience them improves their empowerment and their adjustment to the disease.
 
Web-based systems that can provide electronic-Patient reported Outcomes (e-PRO) have been shown to prompt clinicians to intensify symptom management, to improve symptom control and to enhance patient-clinician communication patient satisfaction, as well as well-being. In addition, it is known that improved communication between patients and medical staff to less anxiety after a biopsy and that anxiety is related to pain.
 
Taken as a whole, these elements encourage the integration of e-health and e-PRO for the management of pain and anxiety in patients undergoing a biopsy. The benefits of e-PRO are still being discussed in terms of quality of life (Qol) and psychological distress. We thus propose to integrate two types of e-health intervention: 1/e-PRO collected by connected objects (smartphone or tablet) as they were used in previous studies, and 2/ e-PRO collected by a phone consultation, which values human communication between the medical staff and the patient.
 
In case of significant pain, the collection of e-PRO by any of these e-health interventions will generate an alert and a reactive and responsive care.
 
In fine, the purpose of this research is to improve the medical organization and care of post-biopsy patients by proposing an innovative connected patient technology, regardless of their remoteness from the hospital.
 
Social inequalities will be reduced by lending a tablet to patients who do not have such a device with a 4G key.

---------------------------------	--

Study Objective(s)	
Primary objective To compare the benefit of intervention by e-health (phone consultation with a professional or connected objects (smartphone or tablet)) with the standard follow up of the pain intensity of patients 4 days (D4) after a breast biopsy.
 
Secondary objectives
 
 - To compare the benefit of intervention by e-health (phone consultation with a professional or connected objects) with the standard follow up of the pain intensity of patients during the consultation of results announcement (about D10) after a breast biopsy. - To compare the benefit according to the type of intervention by e-health (phone consultation with a professional or connected objects) on the pain intensity of patients at 4 days (D4) and during the consultation of results announcement (about D10), after a breast biopsy. - To compare the benefit of intervention by e-health (phone consultation with a professional or connected objects) with the standard follow up of the anxiety intensity of patients at 4 days (D4) and during the consultation of results announcement (about D10), after a breast biopsy. - To compare the benefit according to the type of intervention by e-health (phone consultation with a professional or connected objects) on the anxiety intensity of patients at 4 days (D4) and during the consultation of results announcement (about D10), after a breast biopsy. - To compare the benefit of intervention by e-health (phone consultation with a professional or connected objects) with the standard follow up of the esthetic impact of patients at 4 days (D4) and during the consultation of results announcement (about D10), after a breast biopsy. - To compare the benefit according to the type of intervention by e-health (phone consultation with a professional or connected objects) on the esthetic impact of patients at 4 days (D4) and during the consultation of results announcement (about D10), after a breast biopsy. - To compare the benefit of intervention by e-health (phone consultation with a professional or connected objects with the standard follow up of the insomnia of patients at 4 days (D4) and during the consultation of results announcement (about D10), after a breast biopsy. - To compare the benefit according to the type of intervention by e-health (phone consultation with a professional or connected objects) on the insomnia of patients at 4 days (D4) and during the consultation of results announcement (about D10), after a breast biopsy. - To compare the benefit of intervention by e-health (phone consultation with a professional or connected objects) with the standard follow up of patient's management - To compare the use of a biopsy-related drug intervention (analgesics, anxiolytics, antidepressants, anti-inflammatory and hypnotics) in patients with e-health interventions (phone consultation or smartphone), with the standard follow-up, during the consultation of results announcement (about D10) after a breast biopsy. - To compare adverse events in patients with e-health interventions (phone consultation with a professional or connected objects), with the standard follow-up, during the consultation of results announcement (about D10) after a breast biopsy.
---------------------------	---

	
 - To reduce social and territorial inequalities. - To assess satisfaction with specific study management. - To assess compliance.
Study endpoints	
Primary endpoint: Pain score assessed (by phone) via a numeric pain scale completed 4 days after biopsy (D4).
 
Secondary endpoints :
 
 - Pain score assessed using a numeric pain scale administered after to biopsy and during the consultation of results announcement (approximately D10). - Anxiety score assessed using a numeric anxiety scale administered after to biopsy, at 4 days (D4) and during the consultation of results announcement (approximately D10). - Esthetic impact score assessed using a numeric esthetic scale administered after to biopsy, at 4 days (D4) and during the consultation of results announcement (approximately D10). - Insomnia score assessed using the Index of Severity of Insomnia administered during the baseline visit and the consultation of results announcement (approximately D10). - Number of alerts that generated a phone call or number of phone calls generated directly by the patient and patient care accordingly. - Quantity, nature and dose of analgesics, anxiolytics, anti-depressants, anti-inflammatory and hypnotics used for the biopsy and its aftermath. - Adverse event in particular bleeding and infection due to biopsy recorded at 4 days (D4) and during the consultation of results announcement (about D10) by NCI-CTCAE 5.0 - Geographical distance from the reference center. - Number of tablets/4G keys made available to patients who do not benefit from them at home. - Number of positive responses to satisfaction questions related to the number of solicitations for the study and how interventions are communicated - Rate of completion questionnaire and numeric scale.
Benefit	
Focusing on symptoms as patients experience them improves their empowerment and their adjustment to the disease.
 
e-PRO prompt clinicians to intensify symptom management, to improve symptom control and to enhance patient-clinician communication patient satisfaction, as well as well-being. In addition, it is known that improved communication between patients and medical staff to less anxiety after a biopsy and that anxiety is related to pain.
 
Taken as a whole, all these elements encourage to integrate e-health and e-PRO in the management of pain and anxiety in patients undergoing a biopsy.
 
In case of significant pain, the gathered e-PRO will generate an alert and a reactive and responsive care. In fine, this research aims to improve the medical organization and management of post-biopsy patients by proposing an innovative connected patient technology, regardless of their remoteness from the hospital.

Eligibility criteria	
1) Inclusion criteria
 
 - Patient with diagnostic breast biopsy at ICM - Age > 18 years - Informed patient and signed informed consent received - Affiliation to a social security system 
2) Non inclusion criteria
 
 - Patient without phone number - Patient with previous biopsy in 6 months prior to study - Pregnant and breastfeeding woman - Patient whose regular follow-up is initially impossible for psychological, family, social or geographical reasons - Patient under legal protection (guardianship, curatorship or safeguarding of justice)
Enrolment Procedure	
After the patient has given her informed consent to participate in the study, and after verification of all inclusion/ non-inclusion criteria, the investigator will proceed to the patient registration via a dedicated form to be sent to the Biometrics Unit of the center.

Treatment modalities	
After breast biopsy and randomization (random bloc method and ratio 1:1:1), patients will either be in the:
 
 - Experimental Group 1: PRO gathered via a phone consultation - Experimental Group 2: e-PRO self-completed via connected objects (tablet/phone) - Group 3: Control group without e-PROs (standard care)  
Experimental Group 1 with phone consultation (n=64)
 
Experimental Group 2 with application on connected objects (phone/tablet) (n=64)
 
Group 3 without intervention (n=64)
 
D0 Biopsy R (1:1:1) N= 192
 
D4
 
D10
 
D0 = Randomization + Evaluations of pain, anxiety and esthetical impact (with numeric scale) D4 = Evaluations by phone consultation of pain, anxiety and esthetical impact (with numeric scale) D10 = Evaluations of pain, anxiety and esthetical impact (with numeric scale) during the consultation of results announcement
 
Evaluations of pain, anxiety and esthetical impact (with numeric scale) by phone consultation
 
Evaluations of pain, anxiety and esthetical impact (with numeric scale) via the application on connected objects (phone/tablet)

	
At D1, D2 and D3, patients in the experimental group 1 will receive a call from a neuro-psychologist during which pain, anxiety and esthetical biopsy impact will be assessed using numeric or visual analog scales during a semi-direct interview. During this call, any adverse events related to the breast biopsy will also be noted, as well as the amount, nature and dose of analgesics, anxiolytics, anti-depressants, anti-inflammatory and hypnotics taken linked to the biopsy. If detected, pain or significative distress would be specifically managed.
 
Patients in the experimental group 2 will be asked by SMS or notification to connect to the application in order to complete online the numeric and visual analog scales of pain, anxiety and esthetical impact. Any adverse events related to the breast biopsy will also be noted online, as well as the amount, nature and dose of analgesics, anxiolytics, anti-depressants, anti-inflammatory and hypnotics taken for the biopsy. If detected, pain or significative distress would be specifically managed.
 
At D4 post biopsy, all patients (of the 3 groups) will receive a phone call from a neuro-psychologist to assess pain, anxiety and esthetical impact, using numeric scales, and to collect adverse events. If detected, pain or significative distress would be specifically managed.
 
And at D10 (+/- 3 days), all patients will have the consultation of biopsy results announcement. This visit will be held either on-site or by videoconference. At the beginning of this consultation, pain, anxiety and esthetical impact will be assessed using numeric scales. The adverse events related to the breast biopsy will be collected as well as the amount, nature and dose of analgesics, anxiolytics, anti-depressants, anti-inflammatory and hypnotics taken for the biopsy and its findings. Insomnia will be evaluated by the Insomnia Severity Index. If detected, pain or significative distress would be managed as usually in the center. If the consultation is to be done by telephone, it is essential that this data collection be done before the results are announced.

Statistical considerations	
Sample size.
 
A pilot study has been performed in the radiology department including 25 patients in order to determine the pain level on average: mean = 5 and standard deviation = 3.
 
Assuming a mean pain score on day 4 equals to 5 points with a standard deviation equals to 3 in the control group, with α (two-sided) = 2.5%, power= 90%, it is necessary to include 58 patients per group (174 patients in total), to detect a difference of 2 points (according algology criteria and good practice recommendations) between control arm and each experimental arm. Finally, 192 patients will be included considering 10% non-evaluable patients.
 
Statistical analyses.
 
A statistical analysis plan (SAP) will be written before the closed database. All statistical analyses will be performed on ITT population and on PP (per-protocole) population for primary endpoint. All collected data will be described.
 
Descriptive analyses will be performed using frequency (N) and percentage (%) for categorical variables, mean / standard deviation or median / range for continuous parameters.

	
The Pearson's chi-square or the Fisher's exact test will be performed for categorical variables and the Student test or Wilcoxon / Kruskal-Wallis test for continuous parameters.
 
The primary endpoint, pain score assessed by phone 4 days after biopsy, will be compared between control and experimental arms (telemedicine vs control and smartphone vs control).
 
The secondary endpoints will be compared between control and experimental arms (telemedicine vs control and smartphone vs control) and between the two e-PRO interventions (telemedicine vs smartphone).
 
All statistical analyses will be performed with the Stata software v16.0 and a statistical report will be provided according to the current model.

Study period	
Starting date of inclusion: February 2021 Duration of inclusion: 34 months Duration of participation: 10 days (+/- 2 days) Date of end of patient follow-up: December 2023

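### Two insomnia objectives name D4, but no D4 insomnia measure is planned; in the management endpoint, alerts cannot arise in controls on D1-D3, so testing them against control would partly reflect the design

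*Combined protocol and SAP*

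**What the plan says.** **Insomnia.** Under Study Objective(s), one secondary objective compares e-health "with the standard follow up of the insomnia of patients at 4 days (D4) and during the consultation of results announcement (about D10"), and a second compares the two e-health types "on the insomnia of patients at 4 days (D4) and during the consultation of results announcement (about D10), after a breast biopsy". Under Study endpoints the timing is different: "Insomnia score assessed using the Index of Severity of Insomnia administered during the baseline visit and the consultation of results announcement". The schema under Treatment modalities gives "D0 = Randomization + Evaluations of pain, anxiety and esthetical impact (with numeric scale") and "D4 = Evaluations by phone consultation of pain, anxiety and esthetical impact (with numeric scale"). The text that follows says that at D4 "all patients (of the 3 groups) will receive a phone call from a neuro-psychologist to assess pain, anxiety and esthetical impact", and adds adverse events. The only visit description that mentions insomnia is the D10 consultation: "Insomnia will be evaluated by the Insomnia Severity Index". For analysis, Statistical considerations lists "the Student test or Wilcoxon / Kruskal-Wallis test for continuous parameters" and leaves the detail to a SAP to be written before the database is closed.

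**Patient management.** One secondary objective compares patient management under e-health with standard follow-up. Its endpoint is the number of alerts that led to a call, or the number of calls made by the patient, with the resulting care. Background and Rationale says that alerts are generated by e-PROs collected through the e-health interventions, and that patients are encouraged to call if they suspect a complication. Treatment modalities defines Group 3 as having no e-PROs. Statistical considerations compares the secondary endpoints between each experimental arm and control, and between the two experimental arms.

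**The concern.** An objective that names a time point needs a measurement at that time point. For insomnia at D4 the plan names none, and a later SAP cannot supply data that were not collected. Two objectives would then go partly unanswered.

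The management endpoint has a different weakness. One of its two components is produced by the monitoring that defines the experimental arms. Compared with a control arm that has no such monitoring on D1-D3, that component can differ even if patients are no better or worse off. If it is tested against control, alone or pooled with patient calls, a significant result could be reported as a difference in management when it shows only that the alert system was switched on.

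**Working it through.** **1. Insomnia: the sections side by side**

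| Place | Baseline / D0 | D4 | About D10 |
|---|---|---|---|
| Two insomnia objectives | not named | named | named |
| Insomnia endpoint | named | not named | named |
| Schema, Treatment modalities | not listed | not listed | not listed |
| Visit text, Treatment modalities | not described | not listed | named |

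The endpoint list does name D4 for anxiety and esthetic impact, so its omission for insomnia looks deliberate. The endpoint, schema and visit text agree that there is no insomnia measure at D4; only the objectives differ. Planned D4 insomnia assessments: 0 of 192 patients. The schema omits the D10 index, which the visit text includes, so its silence on the baseline index is weak evidence. The D0 line still needs reconciling with the endpoint.

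**2. D10 insomnia: what the baseline value could add**

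The plan's own sample size first. With difference 2, SD 3, two-sided alpha 0.025 and n per arm, t-test power is 1 - F(t; 2n-2, (2/3)·√(n/2)), where F is the noncentral t distribution function and t the 0.9875 quantile. It is 0.899 at n = 57 and 0.905 at n = 58, which reproduces 58 per group. Then 58 × 1.1 = 63.8, rounded to 64, and 3 × 64 = 192.

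The same formula solved for the standardized difference at n = 58 and 90% power gives 0.66. ANCOVA on the baseline value multiplies the variance by 1 - r² and the detectable difference by √(1 - r²). The correlation r is assumed; the documents do not give one.

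| r | 1 - r² | Variance cut | Detectable difference |
|---|---|---|---|
| 0.3 | 0.91 | 9% | 0.63 |
| 0.5 | 0.75 | 25% | 0.57 |
| 0.7 | 0.51 | 49% | 0.47 |

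The 0.025 level and 90% power are stated for the pain endpoint only and are borrowed here for scale.

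**3. Management endpoint: who can have an alert**

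- Group 1 is phoned on D1, D2 and D3. Group 2 is prompted to complete scales online; that sentence does not repeat the days, which are read from context.
- No control contact is described between D0 and D4, so there are 0 alert-generating contacts in controls on D1-D3.
- At D4 all three groups are phoned. The text does not say whether that call can raise an alert.
- Patient-initiated calls are possible in every arm.

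*Alerts alone.* Against 0/58 in controls, Fisher's exact test (two-sided) gives p = 0.057 for 5/58, 0.027 for 6/58 and 0.013 for 7/58.

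*Pooled any-contact.* Let c be the patient-call rate, equal in both arms (no benefit), and a the alert rate. The control rate is c. The e-health rate is 1 - (1 - c)(1 - a) if alerts and calls are independent, and max(c, a) if they overlap fully. For c = 5% and a = 10% this is 1 - 0.95 × 0.90 = 14.5%, or 10% with full overlap. Enumerating all outcomes with 58 per arm gives the chance that e-health is significantly higher (Fisher, p<0.05):

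| Call rate | Alert rate | Independent | Full overlap |
|---|---|---|---|
| 5% | 5% | 8% | 0.5% |
| 5% | 10% | 28% | 8% |
| 5% | 20% | 79% | 60% |
| 10% | 5% | 6% | 1% |
| 10% | 10% | 20% | 1% |
| 10% | 20% | 63% | 24% |

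All call and alert rates are assumptions.

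**The case against.** **The D4 mismatch may be only carried-over wording.** The anxiety and esthetic objectives have the same form and do include D4. That is the likeliest cause, and it makes the repair easy, but the contradiction remains until one side is changed.

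**ANCOVA is a preference.** Randomized arms can validly be compared at D10 without adjustment, and the SAP still to be written could specify it. This stands: the gain is in precision, and its size rests on an assumed correlation.

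**More triggered contacts under e-health is a real process difference.** The intervention consists of alerts and responsive care, and the objective concerns management. The word joining the two components can also be read as two separate counts. This stands too. The criticism is limited to testing alerts, or a pooled count, against control and reading the result as patient benefit.

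**The illustration is selective.** It reduces a count to any contact versus none and uses a test that the plan does not assign to this endpoint. Independence of alerts and calls is also the less favourable case. The full-overlap column shows how much smaller the problem can be.

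**Stronger readings that the documents do not support.** A reader might infer that the insomnia objectives cannot be answered at all, but the D10 index is planned in two places. A reader might also infer that the management endpoint is zero by construction in controls. It is not: they can call, and they are phoned at D4.

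**Conclusion.** The concern holds in two limited parts.

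First, the plan contradicts itself on insomnia at D4: two objectives name it and no planned assessment provides it. This rests on the text alone. The unadjusted D10 comparison is valid but less precise than one that uses the baseline index the plan already names; the variance saving is 9% to 49% for assumed correlations of 0.3 to 0.7.

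Second, on D1-D3 the alert component cannot arise in controls, so a test of alerts or of a pooled count against control would partly reflect the design. How far depends on alert and call rates, their overlap and whether the counts are pooled, none of which the documents give. With a 5% call rate, the chance of a misleading significant excess runs from 0.5% (5% alerts, full overlap) to 79% (20% alerts, independence). The problem is small if alerts are rare and large if they are common.

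Both parts concern secondary endpoints. The primary endpoint and the sample size are unaffected.

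**What to change.** **Insomnia**
- Delete the D4 time point from both insomnia objectives.
- List the insomnia index at D0, to match the endpoint, recorded before the allocation is known.
- Specify ANCOVA of the D10 index adjusted for the baseline index. If the baseline index was not collected, compare D10 unadjusted and say so.
- Adding the index to the D4 call would also remove the contradiction, at the cost of one more questionnaire.

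**Patient management**
- Do not test alerts against control.
- Report alerts and the resulting care descriptively and separately for Groups 1 and 2. State what counts as an alert-generated call in Group 1, which is already on the phone on D1-D3.
- Compare patient-initiated calls across the three arms, and show total unscheduled contacts by type, because alerts may replace calls.
- State whether contacts arising from the D4 call count.

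**Cost.** Protocol and SAP wording, plus a D0 entry for an index that the endpoint list already names; no new visit. The secondary claims become narrower: no D4 insomnia claim and no alert-versus-control test.

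### The drug-use endpoint rests on an open-label, rule-free attribution to the biopsy, names no time point and lists no D0 medication record; a common all-reasons D10 record with a D0 baseline would be a cheap improvement.

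*Combined protocol and SAP*

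**What the plan says.** The synopsis describes the design as "Monocentric, prospective, open-labeled, randomized controlled trial". Under Study endpoints, the drug-use endpoint is "Quantity, nature and dose of analgesics, anxiolytics, anti-depressants, anti-inflammatory and hypnotics used for the biopsy and its aftermath". It carries no assessment time, although the pain, anxiety, esthetic, insomnia and adverse-event endpoints around it each do.

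The matching entry under Study Objective(s) begins "To compare the use of a biopsy-related drug intervention (analgesics, anxiolytics, antidepressants, anti-inflammatory and hypnotics" and places the comparison "with the standard follow-up, during the consultation of results announcement (about D10) after a breast biopsy".

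Collection is described under Treatment modalities:

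- **D0.** The schema legend reads "D0 = Randomization + Evaluations of pain, anxiety and esthetical impact (with numeric scale"; medication is not listed.
- **D1-D3, Group 1.** "patients in the experimental group 1 will receive a call from a neuro-psychologist", who notes the listed drug classes, "anti-inflammatory and hypnotics taken linked to the biopsy".
- **D1-D3, Group 2.** The patient fills in the application herself: "Any adverse events related to the breast biopsy will also be noted online, as well as the amount, nature and dose of analgesics" and the other classes, limited to those taken for the biopsy.
- **D1-D3, Group 3.** No collection.
- **D4, all groups.** A telephone call covers the scales and adverse events; drugs are not listed.
- **D10, all groups.** Drugs taken because of the biopsy or its findings are collected at the results consultation, with one wording for every arm.

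The Eligibility criteria exclude nobody for regular use of any of the five classes. Statistical considerations plans secondary comparisons of each e-health arm with control and of the two e-health arms with each other.

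**The concern.** Each drug must be judged biopsy-related before it counts. For a woman who already takes a nightly hypnotic, an antidepressant or a daily anti-inflammatory, that judgement can go either way. It is made after allocation, by people who know the arm, and without a rule. If arms differ in how readily a regular drug is put down to the biopsy, equal true intake will appear as a difference in drug use. With no D0 record to compare against, the analysis could not separate continued medication from new medication.

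The drug comparison helps in reading the pain result, because it bears on whether a lower score came with more or less medication. That use is my inference; the synopsis does not state it. Classes that are often taken long term for other reasons are the most exposed.

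**Working it through.** **The plan's own figures.** The plan gives no figure for drug use. Its only calculation is for D4 pain: a difference of 2, SD 3, two-sided alpha 2.5% and power 90%. The normal approximation gives 56 per group and the t-test version 57.1, so the stated 58 is reproduced. Then 3 x 58 = 174 and 174 x 1.10 = 191.4, hence 192, or 64 per arm. Only the 64 is used below.

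**Which entries can reach the endpoint.** The objective points to D10, where collection is common to all arms. The endpoint gives no time and asks for quantity and dose, which daily entries would help to supply. Nothing in the synopsis excludes the D1-D3 entries. If they are used, the e-health arms have up to three extra collections and control has none. The comparison between the two e-health arms would also set interviewer-recorded drugs against self-entered ones.

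**Attribution wording.** It varies: linked to the biopsy (Group 1), for the biopsy (Group 2), for the biopsy and its findings (D10), and for the biopsy and its aftermath (endpoint).

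**Size of a false difference.** The inputs are assumptions, not figures from the documents:

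- b = proportion of regular users, 10% to 30%, equal in all arms
- q1, q2 = probability that a regular drug is attributed to the biopsy in each of two arms, with q1 - q2 = 0.25 to 0.50
- t = proportion with genuine biopsy-related use, equal in all arms and independent of regular use, 0% or 30%

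The proportion counted as users in arm i is 1 - (1 - t)(1 - b x qi). The difference between arms is therefore (1 - t) x b x (q1 - q2).

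| t | b | q1 - q2 | False difference |
|---|---|---|---|
| any | any | 0 | 0 |
| 0 | 0.10 | 0.25 | 0.10 x 0.25 = 2.5 points |
| 0 | 0.30 | 0.50 | 0.30 x 0.50 = 15 points |
| 0.30 | 0.10 | 0.25 | 0.70 x 0.025 = 1.75, about 1.8 points |
| 0.30 | 0.30 | 0.50 | 0.70 x 0.15 = 10.5 points |

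**How often this would look significant.** Take b = 0.30, q1 = 0.50 and q2 = 0.10, with 64 per arm and two-sided 5% (my choice of level).

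- With t = 0, the proportions are 0.30 x 0.50 = 15% and 0.30 x 0.10 = 3%. A normal approximation rejects in about 66% of trials. Summing binomial probabilities over all two-by-two tables with p < 0.05 gives about 71% for the chi-square test and 56% for Fisher's exact test.
- With t = 0.30, the proportions are 1 - 0.70 x 0.85 = 40.5% and 1 - 0.70 x 0.97 = 32.1%. The corresponding rates are about 17%, 17% and 13%.

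**Chance imbalance.** Randomisation balances regular use only in expectation. The 95% range for the difference between two arms of 64 is 1.96 x sqrt(2b(1 - b)/64). This is 10.4 points either way at b = 0.10 and 15.9 points at b = 0.30. A D0 record would let the analysis adjust for it.

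**The case against.** The strongest reply is that the comparison is already common to all arms. Drugs are collected from every patient at the same D10 consultation in the same words, and the objective names that visit. This stands. A reader might infer that a different kind of reporter decides attribution in each arm throughout. The documents do not support that: collection differs by arm only at D1-D3, and Groups 1 and 2 have the D10 collection as well. What remains is that the endpoint does not say D10 is its only source. The D10 attribution is also open label and follows different earlier prompting: interviews in one arm, a form in another, none in control.

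A second reply is that silence in the D0 legend proves little. That is fair. The legend also omits the insomnia index, which Study endpoints requires at baseline, and its D10 line omits drugs, adverse events and insomnia. So the most that can be said is that no D0 medication record is listed, not that none will exist. Even if one exists, the endpoint is not defined against it.

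A third reply is that randomisation balances background use. It does in expectation, and with equal attribution regular use adds noise, not bias. Randomisation does not protect a judgement made after allocation.

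Finally, the documents do not say that the neuro-psychologist filters out regular drugs or that patients over-report them. Direction and size are conjecture, and a difference in any use is a simplification of an endpoint about quantity, nature and dose.

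**Conclusion.** The point holds as a cheap improvement to one secondary endpoint. The endpoint depends on an unblinded attribution without a rule, regular users are eligible, no D0 medication record is listed, and D1-D3 entries collected differently by arm are not ruled out.

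The expected bias is zero if attribution is equal across arms. It is about 2.5 to 15 points in any biopsy-related use if attribution differs by 25 to 50 points and 10% to 30% are regular users. If 30% also have genuine biopsy-related use, it is about 1.8 to 10.5 points. All these rates are assumptions; the documents give none. It would go too far to conclude that the drug comparison is biased as planned, or that nothing in the data could correct it. The primary endpoint and sample size are unaffected.

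**What to change.** 1. At D0, before allocation is opened, record regular use of the five classes in all arms, or confirm that this is already done.
2. At D10, collect every drug in these classes taken since the biopsy, whatever the reason, in the same way in all arms.
3. Base the between-arm comparison on that D10 record. Analyse drugs started or increased since D0, or total use adjusted for D0 use.
4. Keep the stated biopsy-related reason as a descriptive or supportive analysis, so that the objective as written is still reported.
5. State that D1-D3 drug entries are not used for comparisons between arms.

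The cost is one short question at D0 and a reworded endpoint. Some drugs started for unrelated reasons will be counted, at similar expected rates in each arm because of randomisation. That adds some noise but no expected bias.
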